#### D. Data Safety Monitoring Plan:

##### 1. Data Management Plan

Careful training of evaluators will precede study initiation. The main instruments on which training is needed are the baseline Substance Abuse and Service Use Calendar, CAPS

and MOCA. Training of new personnel to conduct the CAPS will contain review of audiotaped ratings as described previously. Training to conduct the MOCA will consist of a training lecture. Training to conduct the Substance Use and Service Use calendars will involve at least five supervised ratings.

Our research group uses Teleforms® software to create, clean and enter data. Forms are created with barcodes that are scanned using Teleforms' object character recognition software. Data is extracted and automatically inputted to an SPSS database.

All forms and samples collected from Veterans will have a study code number but no identifying information. Registration records including the signed consent form will be stored separately from these study records.

Data will be scanned at the site where it is collected at. [name] will import the PDF data uploaded to the study server into central databases at VA Connecticut monthly utilizing Teleforms software. Random patient data will be keypunched into a blank database independently and compared to the scanned data to check for systemic errors. Key data will be independently verified by the research assistant to insure the software is working correctly. Filters flag data that needs to be re-checked by a person such as unclear characters, out-of-range variables and logical inconsistencies. [name] will scan files monthly so that errors can be readily corrected and consequential differences between treatment types (e.g., different levels of attrition) can be monitored closely.

Data quality will be monitored by random inspection of the completed forms by [name] and any problems detected will be discussed with the P.I. Therapists will receive standardized training on the interventions. Adherence to therapies will be monitored using supervision.

## 2. Safety Monitoring Plan:

Participants in Evaluative Component: The risk to Veterans participating in the Evaluative Component who only receive assessments and are not randomized to SBIRT or control is minimal. Only study-related adverse events or study-related serious adverse events impacting these evaluation-only patients will be reported to [name] and if he is unavailable, to [name]. Reports to [name] will include a description of the event and a summary of recent contacts with the patient. [name] will report these to the IRB within three working days.

Participants Randomized in Clinical Trial Component: The risk to Veterans who do go on to be randomized to SBIRT or no-additional-treatment is low (greater than minimal). Veterans with PTSD have a high frequency of medical and psychiatric difficulties. Therefore, changes in medication regimen, the presence of medication side effects and symptom exacerbations are not untoward and do not constitute adverse events. Anticipated adverse events include complaints about the study procedures and the counseling, and any occurrence in which the patient attributes discomfort, harm or disability to the study procedures.

In the clinical trial, assessment for adverse events will be a routine part of every study and therapy visit. SAEs and AEs will be screened for in the timeline follow-backs. Any report that a patient required overnight treatment in any facility (emergency room, detoxification, and hospitalization) will constitute an SAE, as will any report of death or serious disability. Hospitalization or death of another individual due to direct action of patient will also be considered an SAE. When an AE or SAE is reported by a participant, we will refer to the medical chart for additional information.

Any SAEs will be immediately reported to [name] and, if he is unavailable, to [name]. Reports to [name] will include a description of the event and a summary of recent contacts with the patient. This summary will include any warning signs of the adverse event, the patient's general state and any information suggesting a causal link between study participation and the event. [name] will report these to the IRB within 3 working days.

The New England MIRECC's D.S.M.B. will be the D.S.M.B. for this study. The faculty who will be currently on the board are [name], [name] and [name]. All three are NIH-funded investigators with research experience. The D.S.M.B. will be contacted within 3 days about all significant study-related adverse events.

The main risks of the study are frustration with the study procedures, conflict with the study therapist, and exacerbation of PTSD symptoms and/or alcohol use. Because the risk that either therapy would worsen outcomes, no a priori stopping criteria are proposed. Every year, [name] and the D.S.M.B. will review study information on a standardized form. Board members will review recruitment, retention, and follow-up rates for the study-to-date, SAEs and AEs and other data as the D.S.M.B. deems necessary.

Based on this report, each DSMB member will complete a form making one of two recommendations: 1) continue recruitment as planned; or 2) schedule formal DSMB meeting immediately. If any DSMB member recommends a meeting, this will be scheduled within one week, minutes will be kept, the report will be reviewed with the PI, and the committee will vote on whether the study should: 1) continue recruitment unchanged; 2) continue with a protocol amendment; 3) stop recruiting pending further investigation. If, after this meeting, any DSMB member votes to stop recruitment or requests a protocol modification, the Yale IRB will be informed.

A written summary including this information will be provided to the IRB with the protocol renewal. Because the sample size for the Clinical Trial Component study is modest, we are not proposing a preliminary analysis of accumulating efficacy data by treatment assignment.

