#### Justification for Broad Inclusion Criteria and Few Exclusion Criteria:

The inclusion criteria for randomization require that Veterans have enough substance abuse for there to be room for improvement. Veterans with physiological dependence are not excluded because they may benefit from detoxification services available at the participating VA facilities. Veterans who are using drugs or alcohol and are currently in treatment (< 3 times per week) will be randomized because their recent use places them at particularly high risk for discontinuing treatment (Simpson 1982), absent further intervention. Thus they have room to both reduce their substance use and improve their expected treatment attendance.

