## B. Risks

Risks associated with participation in the study include risks associated with:

1. *Completing questionnaires*: Administration of study instruments may be boring, frustrating, or upsetting.

2. *Becoming upset while discussing traumatic events*: There is a risk that individual Veterans will become upset by discussing their traumatic events during assessments or therapy. Veterans report drinking to manage their PTSD symptoms, so there is a risk that upset from discussing traumatic events could lead to increased substance use (Bremner, Southwick et al. 1996). In practice, study-related adverse events in clinical trials of PTSD treatments among Veterans have been very rare (Schnurr, Friedman et al. 2007; Monson, Gradus et al. 2008). Research assistants will emphasize that answering questions is voluntary and will allow Veterans to answer questions at their own pace and without duress

3. *Information from the counseling being told to participants' clinicians at the VA or to someone who reviews their disability application*. The counseling is unlikely to impact the Veteran's disability. The therapist will not volunteer any non-emergent information in the Veterans' chart or to other clinicians, as this is contrary to the voluntary, Motivational Interviewing stance that is integral to SBIRT. The therapist will write a note in the Veteran's VA chart after therapy indicating that the participant was in a research study and met with the therapist.

Nevertheless, the SBIRT therapist is going to convey information to other VA clinicians if the Veteran indicates information during the therapy that requires emergent intervention by another VA clinician. If the Veteran indicates information suggesting imminent danger to the Veteran or to others, the SBIRT therapist will share this information with other VA clinicians so

they can take appropriate action. Therefore, veterans will be told the risk that information that they tell the study therapist may be told to their VA clinicians and would then become available to someone who reviews their disability application.

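### Worsening PTSD or drinking is a named main risk but can fall outside both the AE definition and the DSMB's default annual review; separately, SAE counts do not set planned treatment admissions apart

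*Combined protocol and SAP*

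**What the plan says.** All of this is in the combined protocol and SAP.

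- **Human Subjects D.2, Safety Monitoring Plan, randomized participants.** Because PTSD carries much background illness, "symptom exacerbations are not untoward and do not constitute adverse events". Anticipated adverse events include complaints about the procedures or counseling and "any occurrence in which the patient attributes discomfort, harm or disability to the study procedures". For serious events: "Any report that a patient required overnight treatment in any facility (emergency room, detoxification, and hospitalization) will constitute an SAE". Death and serious disability are also SAEs.
- **Same section, DSMB paragraphs.** The main risks include "conflict with the study therapist, and exacerbation of PTSD symptoms and/or alcohol use". The yearly review covers accrual, retention and follow-up, SAEs and AEs, and anything else the board considers necessary. Notice within 3 days is limited to significant events related to the study. No interim efficacy analysis by assignment is proposed, on the ground that the sample is modest.
- **Human Subjects B, Risks.** On discussing trauma, the protocol accepts that "there is a risk that upset from discussing traumatic events could lead to increased substance use".
- **Justification for Broad Inclusion Criteria.** "Veterans with physiological dependence are not excluded because they may benefit from detoxification services".
- **K.1, Primary Dependent Measures.** The second primary outcome counts weeks with any mental health or substance abuse service use.

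**The concern.** The plan names a harm and describes how it could arise, and then places symptom exacerbations as a class outside the AE definition for the very participants who are randomized. A board that works from its default list sees that harm only where the Veteran attributes it to the study or where it becomes serious. What is at stake is aggregate oversight: a moderate shift in PTSD severity or drinking in one arm need not show up in AE or SAE counts.

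The second matter is independent of the first. The SAE definition draws no line between an overnight stay that signals deterioration and one that is entry into treatment. Where both sit in a single count, the board cannot tell from the count which it is seeing.

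**Working it through.** No formula governs this point and the plan gives no figure to reproduce. The check sets the provisions side by side.

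**Step 1. Routes by which an exacerbation reaches the DSMB without being requested (Safety Monitoring Plan):**

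| Exacerbation | Class | In the default annual review? |
|---|---|---|
| Veteran attributes it to study procedures | AE | Yes |
| Overnight treatment, death or serious disability | SAE | Yes |
| Neither, for example a higher CAPS score or more drinking days | Excluded if it is a symptom exacerbation | No, unless the board asks |

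The third row is the gap. The plan does not say whether heavier drinking counts as a symptom exacerbation. The AE list is introduced as inclusive rather than exhaustive, so staff could record such a change, but nothing tells them to.

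**Step 2. Evenness of the AE route.** AEs are sought at every study and therapy visit. Section E, No-Additional-Treatment Control Condition, gives controls no study therapy, so the SBIRT arm has one more occasion for attribution, and only that arm has counseling to complain about. AE counts are therefore an imperfect basis for comparing the arms on this risk.

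**Step 3. Are the data available?** The Schedule of Assessments has CAPS, BDI-II and the Substance Use Calendar at baseline and weeks 4 and 12. With 160 randomized, that is up to 160 × 2 = 320 post-baseline assessments. The Data Management Plan has forms scanned monthly. It foresees watching for consequential differences between treatment types, but as a study staff task, with attrition as the only example.

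**Step 4. Would an annual table arrive in time to be useful?** The assumptions are even accrual of 160 over the three-year recruitment period given under Feasibility, a first review 52 weeks after the first randomization, and no attrition. Accrual is 160 / 3 = 53.3 a year. Week 12 is counted from the Compensation examination, and baseline falls on that day or up to two weeks earlier, so week 12 comes 12 to 14 weeks after baseline. At the first review, 53.3 × (52 − 14)/52 = 39 to 53.3 × (52 − 12)/52 = 41 Veterans would have reached week 12, and 160 − 53 = 107 would still be to randomize.

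**Step 5. Can one overnight stay be both an SAE and a success?**
- The SAE definition names detoxification and makes no separate class for planned or voluntary stays.
- The eligibility rationale gives possible benefit from detoxification as the reason for keeping dependent Veterans in.
- Section G, Self-Reported Service Use, recognizes that detoxification may be recorded as a medical hospitalization or as substance abuse treatment.
- Section H.1 draws on inpatient files with codes for specialized units, and K.1 excludes no kind of mental health or substance abuse service from an attended week.

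So an overnight detoxification stay is always an SAE and, depending on how it is coded, could also be an attended week.

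**The case against.** **The two statements can be read together.** The exclusion is aimed at background fluctuation, while the listed risk is worsening caused by the study. Attributed harm is an AE, overnight care is an SAE, AEs are also screened in the timeline follow-backs, and the board may request other data. This largely stands. A reader might infer that the DSMB misses the named harm altogether, and the text does not support that. What remains is unattributed, non-serious worsening. The separate pathway for suicidal ideation under Confidentiality protects individuals but gives the board no summary.

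**The DSMB form is not in the documents.** This stands. Only the list of review content can be checked, so nothing can be said about the form's fields.

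**By-arm data.** A reader might infer that the plan forbids any look by arm. It only declines to propose an interim efficacy analysis, and a descriptive safety table is not barred. Nor does the plan say that SAEs are shown by arm, so alarm over the SBIRT arm would be conjecture.

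**Detoxification.** The SBIRT sections refer Veterans to substance abuse or PTSD treatment and offer to walk them to clinic; they do not name detoxification. That SBIRT promotes such stays is an inference. Each SAE report carries a description and any sign of a causal link, so a single planned admission may be recognizable. The difficulty is with the counts.

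**Stopping criteria.** The sentence explaining their absence is visibly incomplete, possibly from text extraction, and carries no weight here.

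**Timing and burden.** With one 60-minute session, an annual table comes too late for those already followed up. Step 4 shows that most Veterans would still be to enroll at a first review. Simply deleting the exclusion could log routine fluctuation as AEs in both arms, and that objection is sound.

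**Conclusion.** The point holds in a limited form. For randomized participants, the AE exclusion and the list of main risks are in tension and must be reconciled. As written, worsening that is neither attributed to the study nor serious is absent from the DSMB's default annual review, although the measures that would show it are scheduled for all 160 Veterans. Separately, SAE totals mix treatment entry with other overnight stays and are hard to interpret.

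No count of unseen exacerbations or of extra SAEs can be derived. A reader might try to size the SAE effect from the 3% in the VA Connecticut chart review. That figure is any VA substance abuse treatment in the three months before the evaluation, among all 62 claimants reviewed. It is not a rate of overnight stays, and it does not describe the randomized population.

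The conclusion rests on reading the listed review content as the default and on detoxification being codable as a substance abuse or mental health service. Power, the estimand and the primary analysis are unaffected. This is an inexpensive improvement to safety oversight.

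**What to change.** 1. Reconcile the AE exclusion with the list of main risks, so that the plan says how worsening of PTSD symptoms or drinking is to be captured. Outright deletion of the exclusion is not proposed.
2. Add to the DSMB's annual review a closed table by coded arm. It should be descriptive, without tests, and not shown to study staff. It should give change from baseline to weeks 4 and 12 in CAPS, BDI-II and days of use, and the number of Veterans worse than baseline at each visit. State that this is safety monitoring and not the interim efficacy analysis that the plan does not propose. The plan describes the yearly review as shared between a named individual and the board, so make the table a separate, board-only part.
3. Keep reporting every overnight stay as now, but tabulate planned or voluntary admissions for substance abuse or PTSD treatment on one line and all other stays on another.

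The cost is protocol and form wording plus one tabulation a year from data already collected. No test is done, so no alpha is spent. The small downside is that the DSMB sees by-arm summaries that include a primary outcome, days of use.

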### **Specific Aims**

The Compensation examination that determines if a Veteran is entitled to any disability payments related to military service is a crucial gateway to accessing VA care for returning OEF/OIF/OND Veterans. However, researchers and oversight agencies have noted that examiners typically do not have guidelines for evaluating comorbid conditions like substance abuse and for referring patients to treatment.

In the Evaluative Component of this study, OEF/OIF/OND Veterans presenting for Compensation evaluations for PTSD will be approached to undergo a paid battery of confidential substance use, PTSD, service use and attitude assessments prior to their scheduled Compensation examinations. The batteries will be collected again twice, four and twelve weeks after the Compensation examinations. Long-term follow-up data will be extracted from VA databases including diagnoses, the results of the Veterans' Compensation evaluations, award determination, use of VA services and attendance at mental health and/or substance abuse treatment.

In the Clinical Trial Component of this study, one hundred sixty Veterans identified during the baseline evaluation as having a substance use disorder will be randomly assigned to a session of Screening, Brief Intervention and Referral to Treatment (SBIRT) or to No-Additional-Treatment.

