3. Power Analysis for Clinical Trial Component: This study is powered to determine whether Veterans assigned to SBIRT have greater probability of attending substance abuse treatment than those assigned to No-Additional-Treatment. A sample size of 128 is sufficient to detect a standardized effect size of the difference in linear trends in probability of treatment attendance by week between treatment and control groups of  $\delta = .50$  with power =  $.80$  and  $\alpha = .05$  (Optimal Design software, version 1.77). Only minimal attrition is expected because VA service use data will be available for Veterans who do not attend any follow-up assessments, although the sample size allows for loss of 20% of participants.

At least a moderate effect size on treatment attendance is expected because Veterans who agree to substance abuse treatment can be escorted to substance abuse treatment at the time of SBIRT therapy. As described in detail in the Facilities Section, the VA facilities in West Haven and Nashville have comprehensive substance abuse treatment and dual PTSD-substance abuse treatment available on demand.

Assuming a conservative standardized effect of .50 on probability of daily substance abuse, a sample size of 128 is sufficient and allows for 20% attrition. An effect size of 0.5 is within the range of effects on substance abuse outcomes reported for SBIRT interventions (Kaner, Beyer et al. 2007). The effect of the SBIRT intervention on slopes of substance use is likely to be substantial if Veterans assigned to SBIRT preferentially avail themselves of available substance abuse and/or PTSD treatment at VA. It is noteworthy that studies of behavioral interventions for PTSD and concomitant substance use reported large effect sizes. For example, Brady and colleagues reported pre- to post-treatment effects of 1.26 for substance use severity when Exposure Therapy was provided to people with PTSD and cocaine abuse (Brady, Dansky et al. 2001). Mean differences and SDs were used to compute a pre-post effect size of .94 for days of alcohol use in a behavioral intervention targeting PTSD and alcohol use among Veterans (Donovan, Padin-Rivera et al. 2001).

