#### H. Chart Review and Database Extraction

1. Therapy Attendance and Service Use Outcomes. Episodes reflecting use of VA substance abuse, specialized PTSD and other mental health treatment will be collected from VA administrative records as described previously (Harpaz-Rotem, Rosenheck et al. 2009). The investigators have extensive experience analyzing VA service use data. [name] is a national authority on service use analyses.

The Austin Information Technology Center provides the service use data for [name] analyses. The Austin databases hold data from all Veterans who received any services from anywhere in VA. The Patient Treatment File contains all episodes of inpatient care delivered within the VA system. The Outpatient Encounter File documents all outpatient VA service use. VA bed section codes indicate hospitalization on specialized units and VA clinic codes indicate outpatient treatment in specialized clinics. In a recent manuscript, [name] describes analysis of psychotherapy service use codes from these databases (Hunt and Rosenheck, 2011), which will be extracted as psychotherapy participation may reflect a more specific measure of engagement in treatment than broader measures.

Service use data will be collected from three months before the Compensation claim was filed until three months after claims adjudication. We will also collect the date Veteran was separated from military service to determine when VA services became available to each Veteran.

2. Compensation examinations of each Veteran will be reviewed by research assistants who will complete a chart extraction form. The extraction form collates the following information:

- i. Clinician diagnosis from C&P exam
- ii. Alcohol Use

-- Level of detail describing alcohol use (No mention, Impression but no number of drinks, or number of drinks---including a statement that there has been no recent use).

- Amount of alcohol reported used in drinks/drinking day
- Alcohol Use Consequence (no mention, consequences listed)
- Alcohol Use Disorder Diagnosed (no diagnosis; use noted but no judgment that it is a problem, or merits intervention; rule-out alcohol use diagnosis made; alcohol use diagnosis made)

iii. Other Substance Use (characterized as for alcohol, with delineation of particular drugs)

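### Serious adverse events in randomized Veterans who miss week 12 are counted only if someone happens to report them, because the plan states no safety check of VA records for these Veterans

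*Combined protocol and SAP*

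**What the plan says.** All references are to the combined protocol and SAP.

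- **Definition.** Human Subjects D.2 treats as an SAE any report of an overnight stay for treatment (emergency room, detoxification or hospital), of death, or of serious disability. Relatedness is not required.
- **Active routes.** Two are named: "In the clinical trial, assessment for adverse events will be a routine part of every study and therapy visit", and "SAEs and AEs will be screened for in the timeline follow-backs".
- **Chart.** For safety purposes D.2 states one use of the medical chart: "When an AE or SAE is reported by a participant, we will refer to the medical chart for additional information".
- **Contacts after baseline.** The Single Patient Flow Chart schedules data collection at weeks 4 and 12. The SBIRT arm also has one counseling session. Under the No-Additional-Treatment Control Condition, controls have no study therapy.
- **VA records.** For the service-use outcome the plan does look past attendance. The Power Analysis for the Clinical Trial Component says: "Only minimal attrition is expected because VA service use data will be available for Veterans who do not attend any follow-up assessments". Section H.1 adds: "Service use data will be collected from three months before the Compensation claim was filed until three months after claims adjudication". The Schedule of Assessments puts this extraction in the middle of year 4.
- **Who sees the count.** D.2 sends SAEs to the D.S.M.B. on a yearly form and to the IRB in a summary at renewal.

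**The concern.** Both active routes need a Veteran who attends, and missing a visit can itself follow from an SAE. A Veteran who has died cannot attend, and one in hospital or in detoxification may not. A participant-report trigger for opening the chart cannot work for that participant's own death.

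The plan treats its two purposes unevenly. A non-attender's VA detoxification stay could count as treatment attendance in the second primary outcome (Data Analysis for Clinical Trial Component, item 1b). The same stay, if overnight, meets the SAE definition but would not reach the SAE count unless someone reported it.

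What is at stake is whether the yearly D.S.M.B. form and the IRB summary describe all randomized Veterans or mainly those who came back.

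**Working it through.** **Step 1: what each attendance pattern leaves unscreened.** Follow-ups are at 28 and 84 days after the examination. Baseline is on the examination day or up to 14 days before it. The SBIRT session is offered straight after the examination or in the next two weeks.

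| Pattern | SBIRT arm | Control arm |
|---|---|---|
| Attends both | Screened | Screened |
| Misses week 4 only | Screened at week 12 | Screened at week 12 |
| Misses week 12 only | Last 84 − 28 = 56 days not screened | Same |
| Misses both | Asked once, at the session; then 84 − 14 = 70 to 84 days not screened | 84 days after the examination, up to 84 + 14 = 98 since randomization, not screened |

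**Step 2: is there another route?** I looked for any other planned use of records or calls that would find an SAE.

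- Section H.2 extracts the Compensation examination report. Item H.6 and the best-estimate procedure (Data Analysis for Evaluative Component, item 2a) use the chart for substance use diagnosis.
- Section G.2 has staff call up to three contacts, to locate the Veteran. No safety question is specified.
- The Data Management Plan watches attrition by treatment, and the D.S.M.B. sees follow-up rates. These show how many Veterans were lost, not what happened to them.

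None is a search of VA records for SAEs.

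**Step 3: how many Veterans?** The plan needs 128 and allows 20% loss: 128 / (1 − 0.20) = 160, which reproduces the planned number. The allowance is 160 × 0.20 = 32. At 10% loss it would be 16, and at 5% it would be 8. The documents give no SAE rate. With assumed rates of 5%, 10% and 20% of Veterans, the expected number with an SAE in the unscreened group is:

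| Lost | 5% rate | 10% rate | 20% rate |
|---|---|---|---|
| 32 | 1.6 | 3.2 | 6.4 |
| 16 | 0.8 | 1.6 | 3.2 |
| 8 | 0.4 | 0.8 | 1.6 |

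These are events occurring in that group, not events missed. Some would be reported by a contact or clinician, some would come up at the SBIRT session, and VA records would recover only the VA-treated part of the rest.

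**Step 4: would the planned extraction help?**

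- *Dates: yes.* The window opens before the claim was filed and closes three months (about 91 days) after adjudication. Adjudication follows the examination, so the window closes after day 84.
- *Scope: not settled.* Section H.1 says of the source file: "The Patient Treatment File contains all episodes of inpatient care delivered within the VA system". What it commits to collect is narrower: "Episodes reflecting use of VA substance abuse, specialized PTSD and other mental health treatment will be collected from VA administrative records". The Specific Aims read more broadly: "use of VA services and attendance at mental health and/or substance abuse treatment". Medical stays are therefore not shown to be in the pull, and no death field is named.
- *Timing: no help to most annual reviews.* The middle of year 4 comes after the three-year recruitment period.

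**The case against.** The strongest reply is that the point hardly matters here. The intervention is one 60-minute counseling session, D.2 rates the risk to randomized Veterans as low, and there is no safety hypothesis or planned comparison of SAEs between arms. An unrelated overnight stay in a control who never returned says little about harm from SBIRT. This stands, and it is why the point is minor.

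Second, the plan works to limit loss. It excludes Veterans who expect not to be able to attend because of incarceration or a move, sends reminders, offers off-site visits, traces through contacts, pays for assessments, and undertakes to follow everyone regardless of retention in treatment. It expects minimal attrition, though partly because VA data stand in for missed visits. Most SBIRT Veterans are likely to be asked at least once: 96% attended a session in the comparable counseling study cited under Feasibility. This also stands. It makes the affected group smaller but does not say what happened to those in it.

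Third, D.2 does not say that the chart is never opened otherwise, and any report counts, whoever makes it. That is correct. However, an unprompted report is chance, and no passage commits anyone to look.

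Fourth, VA records see only VA care, and SBIRT refers Veterans into VA care, so record-found stays could look like an excess in that arm. This is a real limit on any fix and has to be stated with the results.

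**Conclusion.** The gap is real but minor. As written, a VA-treated overnight stay or a death in a randomized Veteran who misses both follow-ups, or who misses week 12 (for the time after week 4), is counted only if someone volunteers it. The number affected is unknown: at most 32 of 160 if the whole 20% allowance were used up in this way. It bears on how complete the safety reporting is and leaves both primary outcomes untouched.

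The documents do not support four stronger readings that a reader might infer:

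- *That a fifth of SAEs will be missed.* The 20% is a sample-size allowance, loss at one visit is not loss at both, and other reports and the SBIRT session are ignored.
- *That the missing events are already in the data being extracted.* The stated commitment covers mental health and substance abuse episodes; medical stays and deaths are not shown to be included.
- *That the Service Use Calendar's 60-day look-back opens a further hole when week 4 is missed.* It limits one instrument. The adverse-event question at the visit and the Substance Use Calendar have no stated limit.
- *That a comparison of harms between arms is biased.* None is planned.

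The conclusion assumes that D.2 is carried out as written and that no unseen form, such as the D.S.M.B.'s standardized one, adds a record check.

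**What to change.** Add two sentences to Human Subjects D.2.

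(a) For each randomized Veteran who misses week 12, with or without week 4, the site investigator or other existing staff who do not collect that Veteran's outcomes will check the VA chart once, after the week-12 window closes. The check covers overnight stays and death since the last completed assessment. Anything found goes through the existing SAE reporting route and onto the annual D.S.M.B. form. The data collector should not do this, because the SBIRT therapist's chart note (Human Subjects B.3) would reveal the arm.

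(b) The planned year-4 VA extraction will include inpatient stays in all bed sections from randomization to week 12 for all randomized Veterans. They will be tabulated by arm and source beside the visit-reported SAEs, without a formal test.

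State the limits with the table: non-VA stays remain unseen, VA capture may be higher under SBIRT, and deaths rest on the chart check because no death field is named.

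The cost is protocol wording, confirmation of the extraction's scope, and a few chart checks. If 32 Veterans missed week 12, at an assumed 5 to 15 minutes each, that is 32 × 5 / 60 = 2.7 to 32 × 15 / 60 = 8 hours over the whole trial. Sample size, visits and the efficacy analysis do not change.
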